6.2. Monitoring

Site monitoring for this study will be provided by the Sponsor or designee. Monitoring oversight will be provided by the Sponsor.

The Site monitors are qualified by training and experience to oversee the progress of the study at the Site and will ensure that the Investigators and their staff understand and adhere to both the applicable regulatory requirements and the study Protocol. In addition, they may assist in resolution of any problems that may arise during the study.

Site Initiation

Site initiation will be performed to assure that each Investigator and his/her staff understands the Protocol, applicable regulations, human subject protection requirements, and the Investigator's obligations. This visit will ensure that required documentation with the appropriate approval is in place prior to Subject enrollment.

Periodic Site Monitoring

Periodic Site monitoring will occur as necessary to ensure continuing adequacy of facilities and adherence to the study Protocol, the GCPs, and applicable regulations and laws that pertain to the conduct of the study. These activities will also review the CRFs and source documentation, the timely submission of accurate records to the Sponsor, and the maintenance of proper records. A report will be written following each Site visit and a follow up letter will be provided to the Site with a summary of findings. Each Site will also be visited at close-out to ensure all documentation is complete.

6.3. Device Accountability and Storage

The Study Device is commercially available in the U.S. and applicable OUS markets. Each Site will manage devices according to their standard process for commercial devices.

6.4. Core Lab

Core Lab services for this study will be provided by a Sponsor designee for study imaging.

6.5. Protocol Deviations

A Protocol deviation is defined as any change, divergence, or departure from the study design or procedures of a research protocol. The Investigator is responsible for promptly recording and reporting Protocol Deviations to the Sponsor and the reviewing IRB/EC per IRB/EC policy. The Sponsor will determine the effect of the protocol deviation on the scientific soundness of the study and Subject safety and determine if additional reports or actions are required. Additional action may include Site retraining, removal of devices from the Site, and/or Site termination.

The Investigator will not implement any changes to the protocol without first obtaining written agreement from the Sponsor and documented approval from the IRB/EC, except in the event of an immediate hazard(s) to a Subject. The Investigator will report the Protocol Deviation in accordance with the applicable regulations.

CONFIDENTIAL INFORMATION

MD133246 Protocol Template

Revision#: 1

Doc Type: GC

6.6. Protocol Amendments

The Investigator will obtain IRB/EC approval on all amendments in a timely manner. The Sponsor will ensure proper training of Investigator and Site staff on all protocol amendments.

6.7. Sponsor Representatives

Sponsor representatives may be present during study procedures to provide technical assistance to the Investigator in the use of the device. The activities of these Sponsor representatives will be supervised by the Investigator.

6.8. Access to Source Data/Documents

Source data are defined as all information necessary for the reconstruction and evaluation of the Clinical Investigation.

The Investigator will keep all study records, source data and investigational devices available for inspection by the Sponsor, Sponsor's monitors, IRB/EC, and regulatory authorities.

6.9. Study Records Retention

The Investigator will maintain complete, accurate and current study records as required by applicable regulatory requirements. Records will be maintained during the study and for a minimum of two years after the latter of the date on which the study is terminated or completed, or the date the records are no longer required to support regulatory approval of the device. In any event, study records will not be disposed of, nor custody of the records transferred, without prior written Sponsor approval.

Investigator records will include, but not be limited to:

- All correspondence with another Investigator, an IRB/EC, the Sponsor, a monitor, or Regulatory Authority, including required reports.
- Records of each Subject's case history and exposure to the device. Case histories include the case report forms and supporting data including, for example, signed and dated consent forms and medical records, including, for example, progress notes of the physician, the individual's hospital chart(s), and the nurses' notes. Such records shall include:
 - Documents evidencing informed consent and, for any use of a device without informed consent, any written concurrence of a licensed physician and a brief description of the circumstances justifying the failure to obtain the informed consent. The case history for each individual shall document that informed consent was obtained prior to participation in the study.
 - All relevant observations, including records concerning adverse device effects (anticipated and unanticipated), the information and date and condition of each Subject upon entering, and information about relevant previous medical history and the results of all diagnostic tests.
 - A record of the exposure of each Subject to the Study Device, including the date and time of each use, and any other therapy.

CONFIDENTIAL INFORMATION

MD133246 Protocol Template

Revision#: 1

Doc Type: GC

- The protocol, any amendments, and documentation of any deviations from the protocol, including the dates and the reasons for such deviations.
- Any other records that Regulatory Authority requires to be maintained by regulation or by specific requirement for a category of investigations or a particular investigation.
- A certification stating that the IRB/EC is in compliance with Regulatory Authority regulations.
- Any other records as required by the Regulatory Authority, the IRB/EC and the Sponsor.

The Investigator will prepare and submit the following reports:

- Withdrawal of IRB/EC approval: The Investigator will report any withdrawal of approval within 5 working days after the Investigator has been notified of the withdrawal.
- Progress reports: Progress reports documenting the procedure, AEs and follow-up data concerning individual Subjects will be submitted to the Sponsor on standardized CRFs. The Investigator may also be required to submit progress reports and final reports to the IRB/EC and to the Sponsor summarizing the Investigator's experience during the study.
- Protocol Deviations shall be reported as described in Section 6.
- Other: Any other reports as reasonably requested by the Sponsor or required by Regulatory Authority.

6.10. Publication Plan

The International Committee of Medical Journal Editors (ICMJE) member journals have adopted a trials-registration policy as a condition for publication. This policy requires that all clinical trials be registered in a public trials registry. The Sponsor will register the study and post results as required by this policy and applicable U.S. laws and regulations.

7. Data Collection and Submission

The Clinical Data Management System (CDMS) for this study will be provided by:

Medidata Solutions Worldwide
[name]
[name]

7.1. Data Collection Methods

This study will report clinical data using the Medidata Rave® CDMS web-based application. The CDMS will be the database of record for the protocol and subject to regulatory inspections. All users will be trained to use the CDMS and will comply with study specific guidelines/instructions as well as applicable regulatory requirements.

Subject data will be collected using protocol-specific case report forms (CRF). Site staff will enter data directly into the CRF for transmission to the Sponsor. The Sites will be notified of any significant amendments to the CRFs.

7.2. Data Clarification and Correction

Once entered, data will be evaluated to ensure that it is complete, consistent and logically sound. If changes to the data in the CDMS are required, all changes, reasons for changes, and persons making the changes will be captured in the CDMS's audit trail.

7.3. CRF Completion Schedule

Case Report Forms will be completed as soon as reasonably possible during or following each Subject visit.

8. Risk Assessment

8.1. Potential Risks

The risks associated with the GORE® VIABAHN® Endoprosthesis for use in in-stent restenosis are expected to be similar to the risks associated with the use of PTA or other endovascular procedures in the superficial femoral artery.

Such risks associated with these devices, including the GORE® VIABAHN® Endoprosthesis include, but are not limited to:

- Hematoma
- Stenosis
- Thrombosis or occlusion
- Distal embolism
- Side branch occlusion
- Vessel wall trauma and/or rupture
- False aneurysm
- Infection
- Inflammation
- Fever and/or pain in the absence of infection
- Deployment failure
- Malposition
- Malapposition
- Device migration
- Device failure

Risks associated with endovascular procedures include, but are not limited to:

- access site infection
- entry site bleeding and/or hematoma
- vessel thrombosis
- occlusion
- psuedoaneurysm
- trauma to the vessel wall including perforation, rupture, or dissection
- distal embolization
- arteriovenous fistula formation
- transient or permanent contrast induced renal failure
- renal toxicity
- sepsis or shock
- radiation injury

CONFIDENTIAL INFORMATION

MD133246 Protocol Template

Revision#: 1

Doc Type: GC

- myocardial infarction
- fever
- pain
- inflammation
- death

The GORE® VIABAHN® Endoprosthesis should not be used in patients with known hypersensitivity to heparin, including those patients who have had a previous incidence of Heparin-Induced Thrombocytopenia (HIT) type II.

8.2. Minimization of Risks

Potential risks associated with the use of the Study Device may be minimized by the following activities:

- The Study Device has been FDA approved for the application being evaluated in this study protocol and for other uses. The Study Device has been CE-marked for the application being evaluated in the study protocol and for other uses.
- The Sponsor has performed qualification testing on the device and device components and appropriate quality control measures have been implemented into production.
- Investigators will be selected who are knowledgeable and experienced in peripheral endovascular procedures.
- Comprehensive Site Investigator and staff training will be conducted to share information regarding design and proper use of the Study Device.
- The Site Investigator, Sub-Investigators, Study Coordinator(s) or designee at each Site will be trained to the protocol and Subject follow-up requirements.
- Protocol inclusion/exclusion criteria and follow-up schedules are designed to select appropriate Subjects and identify potential complications early. Subjects will be assessed post-procedure and subsequently on a regular basis to collect information on the Subject's status and any reportable Adverse Events.
- Data completed by the Sites will be monitored to evaluate protocol compliance and the data for accuracy and Subject safety.
- The Instructions for Use will be provided with the Study Device.

8.3. Summary of Expected Benefits

Subjects may receive no benefit from taking part in this study. The Study Device is expected to improve blood flow in patients with symptomatic peripheral artery disease in the superficial femoral artery.

9. Adverse Events and Safety Monitoring

Adverse Events (AEs) are defined as any untoward medical occurrences in a Subject whether device-related or not.

9.1. Anticipated Adverse Events

Anticipated Adverse Events are complications that are known to be associated with PAD patients undergoing endovascular procedure. See Section 8, Risk Assessment.

9.1.1. Adverse Event Relationship

Each reported AE will be assessed by the Investigator for its primary suspected relationship to the study device, procedure, or disease. Only one primary relationship will be assigned to each reported AE.

Study Device-related

If functioning or characteristics of the study device caused or contributed significantly to the Adverse Event, the AE would be classified as primarily related to the study device.

Study Procedure-related

If the procedure (and not the device) caused or significantly contributed to the Adverse Event, the AE would be classified as primarily related to the index procedure.

Disease-related

If the Adverse Event was a result of the underlying disease progression for which the study procedure is being performed, and not the device or procedure, the AE would be classified as primarily related to the disease.

Not-related

If an Adverse Event which cannot be attributed to the study device, procedure, or disease, it will be reported as "Not related".

Unknown relationship

If the relationship of the Adverse Event to the device, procedure, or disease cannot be determined, it will be reported as "Unknown".

9.1.2. Adverse Event Classification

The severity of each AE will be categorized by the Investigator as either serious or non-serious, as defined below:

Serious Adverse Event (ISO 14155 Definition)

A Serious Adverse Event is an Adverse Event that

- led to death
- led to serious deterioration in the health of the Subject that either resulted in
 - a life threatening illness or injury, or
 - a permanent impairment of a body structure or body function, or
 - inpatient or prolonged hospitalization, or
 - medical or surgical intervention to prevent life threatening illness or injury or permanent impairment to a body structure or a body function
- led to fetal distress, fetal death or a congenital abnormality or birth defect.

CONFIDENTIAL INFORMATION

MD133246 Protocol Template

Revision#: 1

Doc Type: GC

Non-Serious Adverse Events: generally uncomplicated, resolving without intervention, extension of ongoing medical therapy, or consequence to the Subject.

9.1.3. Adverse Event Reporting and Coding

AEs will be reported on the appropriate case report form (CRF) and documented in the Subject's permanent medical record. The Investigator at each Site is ultimately responsible for reporting AEs to the Sponsor.

The following information on each reported Adverse Event will be collected:

- Adverse Event Name
- Adverse Event Onset Date
- Relationship
- Classification Serious or Non-Serious
- Treatment
- Outcome
- Resolution Date

Adverse Events will be coded using the Medical Dictionary for Regulatory Activities (MedDRA). The Sponsor is responsible for the MedDRA classification, along with AE reporting and ongoing safety evaluation of the study in accordance with national regulatory requirements

Adverse Event submission guidelines:

- Adverse Event reporting begins once the patient is enrolled in the study following the final assessment of angiographic eligibility requirements during the study procedure. All Adverse Events should be reported from enrollment through study completion/discontinuation.
- Clinical conditions present pre-procedure are not adverse events unless the severity of the condition worsens during the course of the Subject's participation in the study.
- Provide a diagnosis if possible. If unable to provide a diagnosis, report the symptoms as separate events. Adverse Events should be reported using the full name without abbreviations or narratives.
- Adverse Events with an outcome status of "Ongoing" should be assessed at each follow-up evaluation to determine if the event has resolved. Adverse Events ongoing at study completion/discontinuation should be left as "Ongoing" on the AE case report form.

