4.2. Inclusion Criteria

Potential Subjects must meet all of the following Clinical Inclusion Criteria:

1. Patient is ≥ 18 years old at the time of informed consent signature
2. Patient is willing to give written informed consent
3. Patient has a previously implanted (>30 days) non-covered stent(s) located in the superficial femoral artery
4. Patient has life-style limiting claudication, resting leg pain or minor tissue loss (Rutherford Category 2-5)
5. Patient demonstrates an ABI ≤ 0.9 . If ABI > 0.9 or not measureable, patient is eligible for study if toe-brachial index (TBI) is ≤ 0.5
6. Patient is male, infertile female or female of childbearing potential with a negative beta hCG pregnancy test within 7 days of the index procedure
7. Patient is capable of complying with protocol requirements, including follow-up visits

Potential Subjects must meet all of the following Angiographic Inclusion Criteria:

1. Patient has $\geq 50\%$ in-stent restenosis and/or an occlusion in a previously implanted (>30 days) non-covered stent(s) located in the superficial femoral artery defined as beginning at least 1 cm below the origin of the profunda femoris artery and ending at least 1 cm above the intercondylar notch
2. Patient has a maximum total lesion length of 270 mm, consisting of in-stent and adjacent occlusive disease
3. Patient has a minimum of 1 cm of non-stenosed vessel both proximal and distal to the target lesion(s)
4. Patient has a reference vessel diameter between 4.0 and 6.5 mm
5. The guidewire and delivery system must cross the target lesion(s) intraluminally
6. Patient has a patent popliteal artery ($<50\%$ stenosis) distal to the target vessel
7. Patient has at least 1 patent infrapopliteal runoff vessel ($<50\%$ stenosis) not requiring intervention

CONFIDENTIAL INFORMATION

MD133246 Protocol Template

Revision#: 1

Doc Type: GC

8. Angioplasty balloon can be fully expanded in the target lesion during pre-treatment step

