4.3. Exclusion Criteria

Potential Subjects will not be eligible for study participation if they meet any of the following Clinical Exclusion Criteria:

1. Patient has a known allergy to stent graft components (nickel-titanium or ePTFE)
2. Patient has known allergy to contrast media that cannot be adequately pre-medicated prior to the study procedure
3. Patient with known hypersensitivity to heparin, including those patients who have had a previous incidence of heparin-induced thrombocytopenia (HIT) type II
4. Patient has a known intolerance to anticoagulation or antiplatelet therapy
5. Patient has an uncorrected bleeding disorder (platelet count <80,000/ μ L)
6. Patient has any known coagulation disorder, including hypercoagulability
7. Patient has severe chronic renal insufficiency (creatinine level \geq 2.5mg/dL) within 30 days prior to study procedure unless currently on hemodialysis
8. Patient has septicemia or uncontrolled infection
9. Patient has any planned surgical intervention/procedure within 30 days of the study procedure
10. Patient has major distal amputation (above the transmetatarsals) in the study or non-study limb
11. Patient has prior ipsilateral femoral artery bypass
12. Patient has severe medical comorbidities (untreated CAD/CHF, severe COPD, metastatic malignancy, dementia, etc.) or other medical condition that would preclude compliance with the study protocol or 3-year life expectancy
13. Patient has severe ipsilateral common or deep femoral disease requiring intervention
14. Patient has any previous surgery in the target vessel
15. Patient has had vascular access via the lower extremities within 30 days of the index procedure
16. Patient has had previous target vessel in-stent restenosis treated by relining with another stent
17. Patient is currently participating in another clinical research trial, unless approved by Sponsor

Potential Subjects will not be eligible for study participation if they meet any of the following Angiographic Exclusion Criteria:

1. Patient has untreated flow-limiting aortoiliac stenotic disease
2. Patient has an aneurysm adjacent to the target lesion(s)
3. Patient has perioperative unsuccessful ipsilateral percutaneous vascular procedure to treat inflow prior to enrollment during the index study procedure
4. Patient has femoral or popliteal aneurysm located in the target vessel
5. Patient has non-atherosclerotic disease resulting in occlusion (e.g. embolism, Buerger's disease, vasculitis)

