6. Patient has angiographic evidence of intra-arterial thrombus or atheroembolism from inflow treatment
7. Patient has target lesion access not performed by transfemoral approach

CONFIDENTIAL INFORMATION

MD133246 Protocol Template

Revision#: 1

Doc Type: GC

5. Study Procedures/Evaluations

Any Site staff performing study-specific duties must be qualified by training and experience and must also be appropriately trained on the study protocol and procedures. Delegation of study-specific duties at each Site must be acknowledged by the Site's Principal Investigator and documented on the Delegation of Authority Log.

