All areas that were pre-dilated should be covered with the study device. In addition, the study device should extend into healthy vessel a minimum of 1 cm proximal and distal to the target lesion(s). If overlapping devices is required to ensure complete coverage, there should be at least 1 cm of overlap between devices and device diameters should not differ by more than 1 mm. Post-dilation should be performed after each study device deployment to ensure seating against the vessel wall.

Procedural Completion Imaging

Final post-procedure angiogram will be performed to assess technical results. A post-procedure image is required. This image can be captured during final angiogram (X-ray shot without contrast) or by plain film X-ray. Imaging will be sent to the Core Lab for assessment.

Approved closure devices may be utilized at the Investigator's discretion. If a closure device is not used, sheath removal will be performed in accordance with institutional standard of care. Adequate hemostasis at the arterial puncture site as determined by the Investigator should be achieved prior to discharge.

Adverse events will be collected from the study procedure forward.

Discharge

Prior to discharge, a resting ABI/TBI will be measured. Discharge anti-platelet/anti-coagulation therapy and any additional adverse events will be documented.

Anti-platelet/Anti-coagulation Therapy

The Subject should be discharged and maintained on anti-platelet/anti-coagulation therapy at a dosage deemed appropriate by the Investigator.

CONFIDENTIAL INFORMATION

MD133246 Protocol Template

Revision#: 1

Doc Type: GC

The following medication regime is recommended:

- Dual anti-platelet therapy should be continued for a minimum of 6 months including Clopidogrel 75 mg PO QD (Other members of the thienopyridine class of ADP receptor inhibitors may be prescribed in place of Clopidogrel if subject intolerant to Clopidogrel) and Aspirin 81 – 325 mg PO QD
- Aspirin 81 – 325 mg PO QD should be continued through study follow-up

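### Protocol 5.5 and 9.1.3 start adverse event capture at different moments, and 9.1.3 leaves out early index-procedure SAEs that the primary safety endpoint counts

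*Protocol*

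**What the plan says.** Protocol 5.5 (Procedure) states: "Adverse events will be collected from the study procedure forward".

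Protocol 9.1.3 (Adverse Event Reporting and Coding) states: "Adverse Event reporting begins once the patient is enrolled in the study following the final assessment of angiographic eligibility requirements during the study procedure". The same bullet goes on: "All Adverse Events should be reported from enrollment through study completion/discontinuation". The next bullet sets the baseline: "Clinical conditions present pre-procedure are not adverse events", unless they worsen during participation.

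The primary safety endpoint is procedure- or device-related SAEs within 30 days of the index procedure (Protocol 3.2.2 and 10.1.2; SAP 2.4.2). Both the number of events and the number of subjects with them are tabulated, with a 95% confidence interval. Protocol 9.1.1 attributes procedure-related events to the index procedure and does not exclude its opening part.

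Protocol 5.4 treats a patient as enrolled once every inclusion criterion and no exclusion criterion is met.

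**The concern.** Sections 5.5 and 9.1.3 cannot both govern the site. Between the start of the procedure and the enrollment moment, 5.5 requires collection and 9.1.3 does not. An event in that interval is not a baseline condition under 9.1.3, because it was not present before the procedure. It is not reportable under 9.1.3 either, because enrollment has not happened. The section gives it no status.

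The primary safety result is at stake. Sites could collect different events for the same endpoint, depending on which section they follow. In enrolled subjects the error runs one way: unreported SAEs lower the rate. Acute Procedural Success depends on the same SAEs up to discharge, so it would be raised. In a single-arm study whose primary safety result is a count with an interval, no control arm shares the omission.

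**Working it through.** **1. Does an interval exist between the start of the procedure and enrollment?**

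- Protocol 5.5 describes vascular access, and then the procedural angiography that settles final eligibility. Access therefore comes first.
- Angiographic exclusion criterion 3 (Protocol 4.3) reads "Patient has perioperative unsuccessful ipsilateral percutaneous vascular procedure to treat inflow prior to enrollment during the index study procedure". The protocol thus recognises inflow treatment that takes place within the index procedure and before enrollment.
- 9.1.3 itself places enrollment part-way through the procedure.

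The interval exists on any reading.

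**2. How long is it?** This depends on which text fixes enrollment.

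- *Early reading* (5.5 and 9.1.3: final eligibility is decided at procedural angiography). The interval holds access and any inflow treatment.
- *Late reading* (5.4 with 4.2: every inclusion criterion must be met first). Angiographic inclusion criterion 5 is "The guidewire and delivery system must cross the target lesion(s) intraluminally" and criterion 8 is "Angioplasty balloon can be fully expanded in the target lesion during pre-treatment step". Lesion crossing and pre-dilation then also come before enrollment.

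**3. Which patients are affected?** Only those who are then enrolled. Unsuccessful inflow treatment is an exclusion (criterion 3 above), and so is "Patient has angiographic evidence of intra-arterial thrombus or atheroembolism from inflow treatment" (criterion 6). Those patients leave the study and are not under-counted. On the early reading, what remains is access complications and other inflow injury.

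**4. Does anything visible recover the events?** The Clinical Events Committee items in Protocol 9.2 concern agreement with events as coded or reported by the site. The decision rules that SAP 5.4.2 announces for this endpoint are not visible. They could set a counting window, but they could not restore events that were never collected.

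**5. Scale.** The plan states no figure for this endpoint that could be reproduced. The only input from the documents is n = 108 (Protocol 3.1). The reported and omitted counts below are assumptions, and all 108 subjects are taken as the denominator.

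Step per omitted subject = 1/108 = 0.93 percentage points.

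The intervals are exact (Clopper-Pearson) 95%. For x subjects out of n, the lower limit is the 2.5% quantile of Beta(x, n − x + 1), taken as 0 when x = 0. The upper limit is the 97.5% quantile of Beta(x + 1, n − x).

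| Reported (assumed) | 1 omitted subject restored | 3 omitted subjects restored |
|---|---|---|
| 0/108 = 0.00% (0 to 3.36%) | 1/108 = 0.93% (0.02 to 5.05%) | 3/108 = 2.78% (0.58 to 7.90%) |
| 5/108 = 4.63% (1.52 to 10.47%) | 6/108 = 5.56% (2.07 to 11.70%) | 8/108 = 7.41% (3.25 to 14.07%) |
| 10/108 = 9.26% (4.53 to 16.37%) | 11/108 = 10.19% (5.20 to 17.49%) | 13/108 = 12.04% (6.57 to 19.70%) |

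With no omitted subject, nothing changes. Within each row the intervals overlap.

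**The case against.** The best defence is that the two sections can be harmonised. On this view, the first sentence of the 9.1.3 bullet says for whom reporting is triggered (confirmed-eligible patients, not screen failures). The following bullet puts the baseline at the procedure, in agreement with 5.5. This fails on the bullet's second sentence, which runs reporting from enrollment to the end of participation. That sets a period, not a population.

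A second argument is that the listed AE fields hold an onset date but no time, so the data would not separate events before and after enrollment on the same day. That is true. It means loss occurs only where a site does not enter the event, and 9.1.3 tells sites that reporting has not yet begun.

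Third, monitors review source documents (6.2), database users follow study-specific guidelines (7.1), and the committee's opening remit covers all safety-related and clinical events (9.2). Any of these might catch an omitted event. None is shown to capture events that the reporting rule leaves out.

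Three points stand:

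- The late reading of enrollment is awkward. It would require the delivery system to have crossed the lesion before enrollment, which fits poorly with an intent-to-treat population that includes patients who never received the device (10.6.2). The wider interval is therefore conditional.
- On the early reading, an event must meet several conditions to change the subject-level rate. It must be serious, arise before final eligibility, occur in a patient who is still enrolled, and be that patient's only qualifying SAE.
- No performance goal for this endpoint is visible, so no pass/fail decision is shown to change.

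**Conclusion.** The concern holds. The two start points conflict in current text. Followed as written, 9.1.3 omits procedure-related SAEs from the early part of the index procedure, although the primary safety endpoint includes them.

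Confidence is high for the contradiction and for the direction of the error. The size cannot be derived from the documents: it is 0.93 percentage points for each enrolled subject whose only qualifying SAE is omitted, assuming a denominator of 108. It is zero if no such events occur or if sites apply 5.5. This should be fixed, but it does not by itself undermine the study.

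**What to change.** - Amend Protocol 9.1.3 to agree with 5.5: for every patient who is enrolled, AE capture starts at arterial access for the index procedure and includes events before the enrollment moment.
- State in Protocol 3.2.2 and 10.1.2 and in SAP 2.4.2 that the primary safety endpoint counts procedure-related SAEs from that point.
- Reconcile Protocol 4.2, 5.4, 5.5 and 9.1.3 on one enrollment moment.
- Check the adverse event row of Table 3 (Protocol 5.1) against 5.3, 5.5 and 5.7 in the source document. As extracted, it is marked at Pre-Procedure and blank at 12, 24 and 36 months. This may be a reading fault, and the conclusion does not depend on it.

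The cost is wording in the reporting, endpoint and enrollment text. Eligibility and analysis populations stay as they are. The reported safety figure may become slightly less favourable.
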